[figure not shown]

[figure not shown]
**A Research on the Clinical Significance of Sentinel Lymph Node
Imaging Combined With Imaging Examination in Pelvic and
Peritoneal Lymphadenectomy for Endometrial Carcinoma**

2019.02.01

Study objectives The primary objective of this study is to identify the specific number and percentage of pelvic and abdominal lymph nodes that are invaded by metastatic endometrial carcinoma, and to calculate the coincidence rate of lymph node imaging and pathological examination. By setting up the control group and experimental group, we plan to find out whether pelvic and abdominal lymphadenectomy would exert positive effect on patients with endometrial carcinoma.

Trial design This is a prospective interventional trial. After signing of informed consent, the electronic medical data of patients with endometrial carcinoma will be collected in this study. The specific number and percentage of pelvic and abdominal nodes that are invaded by tumor cells will be calculated. By combining the imaging results and pathological test, we plan to obtain the coincidence rate of three tests. Finally, we would randomize patients into the control group and the experimental group as to receive the pelvic and peritoneal lymphadenectomy. When their postoperative data such as the reoccurrence rate and the five year survival rate are compared, the effect of pelvic and peritoneal lymphadenectomy on the prognosis of endometrial carcinoma are drawn.

Sample size The planned sample size was based on data from a previous study, in which the standard deviation was 5. We assumed an one-tailed α error of 0.05 and a sampling error of 1.0. We propose to enroll 70 participants including 35 patients in the control group and the others in the experimental group, and allow for a dropout rate of 10% for an effective sample size of 60.

Inclusion criteria

1. Volunteer to participate in the study with informed consent;
2. Females aged 10-90 who are confirmed with endometrial carcinoma and are willing to receive primary non-reserved fertility function surgery.

Exclusion criteria

1. Pregnancy, lactation, postmenopause, or planned pregnancy within two years;
2. Suspected or identified as other tumors of genital tract;
3. History of hyperparathyroidism, infectious diseases (tuberculosis, AIDS), autoimmune diseases, or digestive system diseases (malabsorption, crohn disease and dysentery);
4. Other diseases or heavy injuries that will interfere with the results;
5. Simultaneous participation in another clinical study with investigational medicinal product(s) or researcher thinks the subjects are not suitable for this trial.

Withdrawal Subjects must be withdrawn from the study when one of the following criteria occurs:

1. At their own request. At any time during the study and without giving reasons, a subject may decline to participate further. The subject will not suffer any disadvantages as a result;
2. In the investigator's opinion, continuation of the study treatment would be harmful to the subject's health;
3. Obvious non-compliance;

4. Lost to follow-up;
5. Pregnancy;
6. Other medical or surgical treatments of endometrial carcinoma.

Safety assessments

Safety will be assessed by renal and liver function test, electrolyte, routine blood test. Other indicators are detected during the operation and rehabilitation period. The occurrence of any adverse events in participants will be recorded in the case report forms during each patient visit. We will withdraw patients who have severe adverse events, as it is unsafe for them to continue the trial. Meanwhile, we will give them relevant medical care and follow them up until the reaction has terminated.

Statistic analysis

The specific number and percentage of pelvic and abdominal lymph nodes that are invaded by tumor cells are collected. Multiple linear regression analysis was applied to evaluate the risk of lymphatic metastasis related to fourteen independent variables including four qualitative variables (hypertension, diabetes, diagnosis according to the FIGO staging system and the pathological tumor type) and eight quantitative variables (age, BMI, the number of lymph nodes, the interval between biopsy and operation, surgical time, surgical bleeding, postoperative anticoagulant time, preoperative value of Hb, preoperative value of RBC and preoperative value of Hct). All statistical analyses were performed by SPSS 17.0 software package and the level of statistical significance was set at $P < 0.05$. All independent variables were incorporated into the model using the method of "Enter". Data are presented as mean \pm standard deviation. Meanwhile, we collect the lymph node imaging results and the pathological test results so as to investigate the coincidence rate of the three examinations by chi test. As to the analysis of the lymphadenectomy on patients, we would conduct corresponding statistical method to interpret the follow-up data.

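### The coincidence rate sets sentinel node imaging against tumour pathology without a scoring rule; if an imaged node counts as positive, correct mapping is penalised, and on any reading the method's accuracy is not shown

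*Combined protocol and SAP*

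**What the plan says.** The title names two index methods: sentinel imaging ("A Research on the Clinical Significance of Sentinel Lymph Node") and a further, unspecified imaging examination ("Imaging Combined With Imaging Examination in Pelvic and").

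The Study objectives section makes it part of the primary objective "to calculate the coincidence rate of lymph node imaging and pathological examination", without saying which imaging is meant. The Trial design section widens this: "By combining the imaging results and pathological test, we plan to obtain the coincidence rate of three tests". The Statistic analysis section says that imaging and pathology results are collected "so as to investigate the coincidence rate of the three examinations by chi test".

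Pathology is described only as tumour invasion of nodes: "The specific number and percentage of pelvic and abdominal nodes that are invaded by tumor cells will be calculated".

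The document does not list the three tests. It does not define a positive or negative result for any of them, and it does not state the unit (node, region or patient). It does not say how an imaged but tumour-free node, or a patient in whom mapping fails, is scored. It plans no detection rate, sensitivity or negative predictive value. The Sample size section rests on something else ("The planned sample size was based on data from a previous study, in which the standard deviation was 5", variable not named) and gives no expected coincidence rate.

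**The concern.** For the imaging examination, agreement with pathology is meaningful, because a reader can call a node suspicious or not and pathology can confirm or refute the call. Sentinel imaging gives no such call. In the ordinary sense of the term, it shows which node drains the tumour first. The diagnostic information is the pathology of that node, and the question is whether it reveals the nodal status of the patient.

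An agreement rate that treats the map itself as a test result therefore measures the wrong thing. Scored per node, every mapped clean node is a disagreement. Scored per patient, every mapped patient with clean nodes is a disagreement, while an unmapped patient with clean nodes agrees although the method failed. Replacing the chi test with kappa or a McNemar test would not help, since the fault lies in what is compared.

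At stake is a component of the primary objective and the only planned measure of the method named in the title.

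**Working it through.** **Figure to reproduce.** There is none. The document states no expected coincidence rate, detection rate or proportion node-positive, so every input below is an assumption shown over a range.

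**Which three tests.** The title supplies two imaging methods, and pathology is the third. Without sentinel imaging only two tests are named. Its inclusion is an inference, but a strong one.

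**Per node, imaged = positive.** Let N be nodes removed, M invaded, K imaged, and T both imaged and invaded. Agreements are the T imaged-invaded nodes plus the N − K − (M − T) nodes that are neither, so

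agreement = (N − M − K + 2T)/N.

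With nothing imaged it is (N − M)/N. The difference is (2T − K)/N, which is negative whenever T/K < 1/2, that is, when fewer than half of imaged nodes are invaded. This does not require mapping to be independent of metastasis.

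Assume 60 patients, 20 nodes each, 3 sentinel nodes each, and 15% node-positive with one sentinel and one non-sentinel node invaded. Then N = 1200, K = 180, M = 18 and T = 9.

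- Perfect mapping (every node-positive patient found): (1200 − 18 − 180 + 18)/1200 = 1020/1200 = 85.0%.
- No node mapped in anyone: (1200 − 18)/1200 = 98.5%.
- Varying nodes from 15 to 30 and sentinel nodes from 2 to 4 per patient: perfect mapping runs from 660/900 = 73.3% to 1680/1800 = 93.3%; no mapping from 882/900 = 98.0% to 1782/1800 = 99.0%.
- Varying the node-positive share from 5% to 30% (M = 6 to 36): perfect mapping stays at 85.0%, because M = 2T in this set-up; no mapping runs from 1194/1200 = 99.5% to 1164/1200 = 97.0%.

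**Per node, partial detection.** Assume 20 nodes, k = 2 sentinel nodes, p = 0.15 with one invaded node, which is a sentinel node with probability s = 0.90 when mapping succeeds. With detection rate d, the expected disagreements per patient are (1 − p)kd + p{d[s(k − 1) + (1 − s)(k + 1)] + (1 − d)}. For d = 0.60, 0.80 and 0.95 these are 1.188, 1.534 and 1.7935. Dividing by 20 and subtracting from 1 gives agreement of 0.941, 0.923 and 0.910. The direction is the same, but the fall is only about 3 percentage points.

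**Per patient, any imaged node = positive.** With mapping independent of metastasis, agreement = dp + (1 − d)(1 − p), whose slope in d is 2p − 1.

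| p | d = 0.60 | d = 0.80 | d = 0.95 |
|---|---|---|---|
| 0.05 | 0.41 | 0.23 | 0.095 |
| 0.15 | 0.43 | 0.29 | 0.185 |
| 0.30 | 0.46 | 0.38 | 0.32 |
| 0.50 | 0.50 | 0.50 | 0.50 |
| 0.60 | 0.52 | 0.56 | 0.59 |

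With all 60 patients mapped and 9 node-positive, agreement is 9/60 = 15%.

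**A different rule: sentinel node pathology against full-dissection pathology.** In mapped patients, agreement = 1 − p(1 − sensitivity). At p = 0.15 it is 0.970, 0.985 and 0.993 for sensitivity 0.80, 0.90 and 0.95. Over p from 0.05 to 0.30 and the same sensitivities, it lies between 0.940 and 0.998. If unmapped patients count as failures (p = 0.15, sensitivity 0.90), it is d × 0.985 = 0.591, 0.788 and 0.936 for d = 0.60, 0.80 and 0.95, so it rises with mapping.

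**The case against.** The strongest objection is that the plan never says an imaged node counts as metastatic. A reader might infer from the objective that this is the sponsor's rule and that better mapping must therefore score worse. The document does not support that inference, because it states no scoring rule at all. The objective speaks of lymph node imaging, which could mean only the separate imaging examination. A combined read, in which sentinel imaging locates the node and the examination judges it, is not excluded. Nor is sentinel node pathology against full dissection, under which the score can rise with mapping.

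This stands, and it makes the reversal conditional on three things: the scoring rule, fewer than half of imaged units being invaded, and inputs the document does not give. Between detection rates of 60% and 95% the per-node fall is also modest.

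The alternatives do not rescue the endpoint, however. If only the imaging examination is meant, the method in the title has no endpoint and the reference to three tests is unexplained. A combined read gives one figure in which the contribution of sentinel imaging cannot be separated. If sentinel node pathology is meant, overall agreement is dominated by node-negative patients: at p = 0.15, a method that misses one node-positive patient in five still scores 97.0%.

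**Conclusion.** The concern holds in a conditional form. What is certain is that this component of the primary objective lacks a definition of a positive result, a unit of analysis and a rule for failed mapping, and that no accuracy measure for sentinel imaging is planned. What is very probable is that sentinel imaging is one of the three tests.

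On the plain reading, imaged = positive, the rate rewards failure to map: 85.0% for perfect mapping against 98.5% for none per node (73–93% against 98–99% over the assumed node counts), and 15% agreement per patient when everyone is mapped. These sizes rest on assumed node counts and an assumed 15% node-positive share; the direction requires that fewer than half of imaged units be invaded.

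On every reading considered, the rate does not show whether sentinel imaging identifies node-positive patients. This should be corrected before the endpoint is analysed.

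**What to change.** 1. Name the three tests, and define a positive and a negative result for each.
2. Keep the coincidence rate only for the imaging examination's positive/negative call against pathology, with the unit stated.
3. Give sentinel imaging its own per-patient endpoints:
   - (a) detection rate in all patients in whom mapping is attempted, in either arm, with failed mapping counted as failure (this needs no dissection);
   - (b) sensitivity and negative predictive value of sentinel node pathology for any nodal metastasis, in mapped patients who have lymphadenectomy, with exact confidence intervals and the number of unmapped patients reported alongside.

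**Cost.** Protocol wording, and a sentinel/non-sentinel label on nodes that are removed and examined anyway. This assumes the sentinel node can still be identified at pathology; the document does not describe specimen handling, so this should be confirmed. No new procedure is needed.

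**Downside.** Precision will be poor. The Trial design section randomises around lymphadenectomy. If only one arm of 35 is dissected, an assumed 15% gives 35 × 0.15 = 5.25, about 5 node-positive patients; 5% to 30% gives 1.75 to 10.5. Even if all 5 were detected, the exact two-sided 95% lower limit for sensitivity would be 0.025^(1/5) = 0.48. That limitation already exists in the data; the present rate conceals it.

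### The title asks about sentinel node imaging used together with other imaging, but the plan gives only undefined coincidence rates and no combined result or accuracy measure, so the combination is not evaluated

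*Combined protocol and SAP*

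**What the plan says.** The title describes sentinel node "Imaging Combined With Imaging Examination in Pelvic and" abdominal node surgery, so its subject is two imaging sources used together.

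Three places say what will be done with the test results:

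- Study objectives: "to calculate the coincidence rate of lymph node imaging and pathological examination", a two-way comparison.
- Trial design: "By combining the imaging results and pathological test, we plan to obtain the coincidence rate of three tests".
- Statistic analysis: imaging and pathology results are collected "so as to investigate the coincidence rate of the three examinations by chi test".

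Coincidence rate is not defined in any of them. The three tests are not listed; the natural reading is sentinel imaging, the imaging examination (conventional imaging below) and pathology. No section gives the unit (patient, side or node), a rule for calling the two imaging sources jointly positive, or an accuracy measure against pathology.

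The plan has other outputs. It counts invaded nodes ("The specific number and percentage of pelvic and abdominal nodes that are invaded by tumor cells will be calculated"), fits a regression for metastasis risk, and compares prognosis between arms ("When their postoperative data such as the reoccurrence rate and the five year survival rate are compared"). None of these describes test performance.

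**The concern.** The value of adding one examination to another depends on whether the two miss the same patients. If they do, combining them gains nothing. If they miss different patients, the gain in detection can be large. A plan about a combination therefore needs a statistic that responds to this overlap in the right way, and it needs pathology as the reference rather than as one of three equal tests.

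If coincidence means that all three agree, a metastasis seen by one examination and missed by the other counts as non-agreement. Yet that is the patient for whom combining helps. If coincidence means something else, the overlap may not enter at all. Either way the study could finish with its test results in hand and no planned answer to the question in its title. A positivity rule chosen after the data are seen (either, both, or some pooling) could be chosen to suit the result.

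**Working it through.** **The plan's own figures.** The documents give no agreement, accuracy or node-positive rate, so there is no planned figure to reproduce on this point. The sample-size inputs (a value "in which the standard deviation was 5", one-tailed 0.05, sampling error 1.0) give (1.645 × 5 / 1.0)² ≈ 67.6, or 68, close to the 70 stated. They do not concern agreement or accuracy.

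**Step 1: what each reading of coincidence can see.** Assume 60 patients, 10 node-positive, each imaging test finding 6 of the 10, and no false positives. Vary only the number of metastatic patients found by both tests.

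| Quantity | Found by both = 6 | Found by both = 2 |
|---|---|---|
| Found by at least one | 6 + 6 − 6 = 6 | 6 + 6 − 2 = 10 |
| Either-positive sensitivity | 6/10 = 60% | 10/10 = 100% |
| All three agree | (50 + 6)/60 = 93.3% | (50 + 2)/60 = 86.7% |
| Each test agrees with pathology | (50 + 6)/60 = 93.3% | (50 + 6)/60 = 93.3% |
| Positive rates (test, test, pathology) | 6/60, 6/60, 10/60 | 6/60, 6/60, 10/60 |

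Three-way agreement falls as the combination detects more. Pairwise agreement and the positive rates do not change, so a chi test on those rates would be the same in both columns.

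**Step 2: size in node-positive patients.** Assume sensitivity s = 0.6 and specificity 0.90 for each examination.

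- Independent errors: three-way agreement s² = 0.36; either-positive sensitivity 1 − (1 − s)² = 1 − 0.16 = 0.84; either-positive specificity 0.90² = 0.81.
- Fully redundant errors: three-way agreement 0.60; sensitivity 0.60; specificity 0.90.
- Range for s from 0.5 to 0.7, independent errors: three-way agreement 0.25 to 0.49; either-positive sensitivity 0.75 to 0.91.

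**Step 3: all patients.** Add an assumed node-positive rate of 15%.

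- Three-way agreement: independent 0.15 × 0.36 + 0.85 × 0.81 = 74.25%; redundant 0.15 × 0.60 + 0.85 × 0.90 = 85.5%.
- Of the 11.25-point gap, 0.85 × 0.09 = 7.65 points come from discordant false positives and 0.15 × 0.24 = 3.6 points from complementary detection.
- Overall correct classification by the either-positive rule: independent 0.15 × 0.84 + 0.85 × 0.81 = 81.45%; redundant 85.5%.
- Independent errors give the better overall accuracy only when p × 0.24 > (1 − p) × 0.09, that is p > 0.09/0.33 ≈ 27%.

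Below that rate, agreement and overall accuracy fall together; they part only above it. The contrast in Step 2 is therefore about sensitivity.

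**The case against.** The strongest reply is that the plan does compare imaging with pathology. The two-way rate in the objectives does so, and if the imaging named there were a pooled result, that rate would be a crude check of the combination. This stands as a possibility, but the text never says the result is pooled and gives no pooling rule. Even then, overall agreement is driven by node-negative patients: in the Step 1 example, a test that found no metastasis would still agree in 50/60 = 83.3%.

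Second, the title may mean only that both examinations are used, and the objectives promise no combined accuracy. That is fair as a reading of the title. But the design section also speaks of combining results, and the plan gives the reader no other way to judge the pairing.

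Three stronger conclusions are tempting, and the documents do not support them:

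- *That a three-way coincidence rate is the only planned parameter.* The objectives have the two-way rate, and node counts, a regression and prognosis outcomes are planned as well.
- *That the plan counts every complementary finding as disagreement.* This holds only if coincidence means that all three agree, and the term is undefined. Under pairwise agreement such a finding is a miss for one test only; under a comparison of positive rates it is ignored.
- *That the statistic moves in the wrong direction in general.* It does so for sensitivity. For overall accuracy on the assumed inputs, it does so only above a node-positive rate of about 27%, and the documents state no rate.

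**Conclusion.** The concern holds in this form: the test statistics are undefined coincidence rates, no combined result or accuracy measure against pathology is specified, and under each of the three-test readings examined the combination is not evaluated. That conclusion rests on the text and not on any assumed number.

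The size is illustrative. With sensitivity 0.6 each, three-way agreement in node-positive patients is 36% or 60%, and either-positive sensitivity is 84% or 60%, for independent and fully redundant errors respectively. The independent case costs nine points of specificity (0.90 to 0.81). The actual figures depend on accuracies, overlap and a node-positive rate that the documents do not give.

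This should be changed before analysis. It goes beyond missing detail, because the stated statistic should be replaced by one that answers the question from results already being collected.

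**What to change.** In the objectives and the Statistic analysis section:

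1. Name nodal pathology as the reference and the patient as the unit.
2. Define a positive sentinel imaging result as an imaging call, kept separate from the node pathology that forms the reference. Define a positive conventional imaging result.
3. Prespecify one combined result, for example positive if either is positive.
4. In patients with nodal pathology, report sensitivity, specificity and negative predictive value with exact confidence intervals for each examination and for the combination.
5. Add a paired (McNemar-type) comparison of the combination with conventional imaging alone, presented as estimation. An either-positive rule cannot miss a metastasis that conventional imaging finds, so discordant pairs among node-positive patients all go one way. The useful result is the size of the gain in sensitivity, set beside the loss in specificity.
6. Keep the three-way coincidence rate as descriptive only, with its definition stated.

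**Cost.** Wording, agreed definitions of a positive imaging call, and one derived variable; no new procedures. An either-positive rule cannot raise specificity and usually lowers it, so both must be reported.

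Precision will be poor. At an assumed node-positive rate of 10–20%, 60 patients give 60 × 0.10 = 6 to 60 × 0.20 = 12 positives. If only one arm of 35 has nodal pathology, which the protocol leaves unclear, there would be 3.5 to 7. For scale, 6 detected of 10 has an exact 95% interval of about 26% to 88% (Clopper–Pearson: the values of p at which P(X ≥ 6) and P(X ≤ 6) each equal 0.025, with n = 10).

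### The title asks about node imaging in lymphadenectomy, but the plan describes no use of imaging in the randomisation or in the recurrence and survival comparison

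*Combined protocol and SAP*

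**What the plan says.** The title begins "A Research on the Clinical Significance of Sentinel Lymph Node" and continues "Imaging Combined With Imaging Examination in Pelvic and" peritoneal lymphadenectomy. The plan then has two parts.

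- **Imaging.** Study objectives and Trial design call for a coincidence rate between imaging and pathology. The Statistic analysis section says this will "investigate the coincidence rate of the three examinations by chi test".
- **Randomised comparison.** Trial design states: "Finally, we would randomize patients into the control group and the experimental group as to receive the pelvic and peritoneal lymphadenectomy". Under Study objectives, the purpose of the two groups is an overall one: "we plan to find out whether pelvic and abdominal lymphadenectomy would exert positive effect on patients with endometrial carcinoma". The outcomes are named in Trial design: "When their postoperative data such as the reoccurrence rate and the five year survival rate are compared". The analysis is left open: "we would conduct corresponding statistical method to interpret the follow-up data".

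The main inclusion criterion is "Females aged 10-90 who are confirmed with endometrial carcinoma and are willing to receive primary non-reserved fertility function surgery". Neither the inclusion nor the exclusion criteria mention imaging findings, so imaging-positive and imaging-negative patients can both enter. The one regression that is specified has lymphatic metastasis as its outcome, and the imaging result is not among its listed variables.

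**The concern.** Agreement with pathology shows how well imaging reads the nodes. It does not show whether the imaging result says anything about the effect of lymphadenectomy on prognosis. Only the randomised arms could bear on that, and the plan does not bring imaging to them. As written, the trial would deliver an agreement figure and one overall arm effect, with no planned link between them, under a title that suggests a link.

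There is also a practical risk. Imaging-positive patients may be few, and no stratification is described. They could fall unevenly between arms, which weakens any later look at that group. If imaging status is prognostic, it also adds avoidable chance imbalance to the main comparison.

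**Working it through.** **The plan's own figure.** Sample size gives SD 5, one-tailed alpha 0.05, sampling error 1.0 and 70 patients, 35 per group. A single-sample precision formula comes close: (1.645 × 5 / 1.0)² = 67.6, so 68, if dropout is ignored. The stated effective size of 60 does not follow from 10% dropout, since 70 × 0.9 = 63. Nothing in this calculation refers to recurrence, survival or imaging.

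**Chance imbalance.** The documents give no imaging-positive rate. Assume 10% to 20%, that is K = 7, 10 or 14 positives of 70. With 35 per arm and no stratification, the number X falling in one arm is hypergeometric:

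P(X = k) = C(K, k) × C(70 − K, 35 − k) / C(70, 35).

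Probability that the arms differ by at least 4 positives:

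- K = 7 (splits 6 v 1 and 7 v 0): 2 × (0.0474 + 0.0056) = 0.106.
- K = 10 (7 v 3 or worse): 2 × (0.1109 + 0.0353 + 0.0062 + 0.0005) = 0.306.
- K = 14 (9 v 5 or worse): 2 × (0.1186 + 0.0497 + 0.0141 + 0.0026 + 0.0003) = 0.371.

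The cut-off depends on parity. For an odd K, at least 4 means at least 5, so K = 8 gives 0.26 and K = 9 gives 0.15. With permuted blocks of size 4 within strata, the difference in a stratum cannot exceed 2.

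**What balance buys.** Assume recurrence of 50% in control and 20% in experimental imaging-positive patients. The 95% half-width for the risk difference is 1.96 × √(0.25/a + 0.16/b), with a controls and b experimental patients.

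| Split (a v b) | Half-width, percentage points |
|---|---|
| 5 v 5 | 56 |
| 7 v 3 | 58 |
| 3 v 7 | 64 |
| 7 v 7 | 47 |
| 9 v 5 | 48 |
| 5 v 9 | 51 |

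The width comes mainly from the small numbers; the split adds little.

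**Interaction.** Take the stated 60 evaluable patients, 30 per arm, and positive shares of 10%, 20% or 30%, giving 3, 6 or 9 imaging-positive patients per arm. Keep 50% v 20% in positives and assume 10% v 10% in negatives. The variance of the difference in risk differences is 0.41/n₊ + 0.18/n₋, with n₊ and n₋ the positives and negatives per arm.

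At 20%: 0.41/6 + 0.18/24 = 0.0758, SE 0.275, 0.30/0.275 = 1.09, and one-sided power is Φ(1.09 − 1.645) = 0.29. At 10% and 30% the power is 0.20 and 0.36. For 80% one-sided power the total would be about 592, 314 or 224 patients at 10%, 20% or 30%. These are normal approximations and crude at such counts.

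**The case against.** Four points can be made for the plan as written.

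1. **The plan is silent; it does not exclude imaging.** A reader might infer that lymphadenectomy is allocated without regard to imaging and that the two kinds of patient will be averaged. The documents do not say so. No randomisation method is given and the follow-up analysis is unspecified. The supportable statement is that no use of imaging is described. This stands. However, an analysis chosen after the data are seen has neither prespecification nor stratification behind it.
2. **The written objectives do not ask the treatment-by-imaging question.** They ask for node counts, agreement and an overall lymphadenectomy effect. The last is a legitimate estimand in a mixed population, and randomisation protects it. This stands too: the mismatch is between the title and the objectives, and the randomised comparison is not invalid.
3. **Stratifying would not answer the title question.** Correct. Under the assumptions above, interaction power is 20% to 36%, and the imaging-positive interval is very wide whether or not the arms are balanced. The change protects balance and allows an honest exploratory report, and no more than that.
4. **Feasibility is not established.** The title names two imaging components, and the documents do not say when either is read relative to allocation, or what the control group receives. A stratum therefore needs a defined source and a rule for discordant results, and an imaging-positive contrast cannot be interpreted until the control condition is stated.

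**Conclusion.** The point holds in limited form. The plan uses imaging only for agreement with pathology and describes no role for it in randomisation or in the recurrence and survival comparison. The overall arm effect remains valid, but as written it does not bear on the imaging question in the title.

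The chance of a difference of at least 4 imaging-positive patients between arms is about 11%, 31% or 37% for 7, 10 or 14 positives of 70. Those counts are assumptions, and the figures shift with odd and even counts.

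A reader might go further and infer that the trial is invalid, or that stratifying would let it decide whether imaging should guide lymphadenectomy. The documents support neither. The stated objective is an overall effect, and at 70 patients any result by imaging status would be exploratory.

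**What to change.** 1. Define one binary imaging status, node-positive or node-negative, from the imaging available before allocation. Say which examination or examinations define it and give a rule for discordant results.
2. Stratify the 1:1 randomisation on that status, using small permuted blocks within the two strata.
3. Adjust the prognosis comparison for the stratum. Report the arm difference with 95% CI in each stratum and the arm-by-imaging interaction estimate, all labelled exploratory.
4. State that conclusions are limited to imaging-pathology agreement and an overall lymphadenectomy effect, and that 70 patients cannot establish whether imaging should guide lymphadenectomy.
5. If imaging cannot be read before allocation, use it only as an adjustment covariate, provided its reading is not influenced by arm, and narrow the title and conclusions in the same way.

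The operation, and the care of imaging-positive patients in either arm, remain for the investigators to define.

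**Cost.** A two-stratum randomisation list and one extra table, with no extra patients or examinations. Imaging must be reported before allocation, and the imaging-positive interval will be very wide.
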